### ***Materials and Methods***

The **primary objective** of this study is to evaluate the efficacy of combining intense therapeutic ultrasound (ITU) with standard care, including post-treatment therapy, exercises and boot immobilization for the treatment

of chronic plantar fasciitis/osis. A **secondary objective is to** evaluate the tolerability and safety of intense therapeutic ultrasound in the treatment of plantar fasciitis.

These objectives will be accomplished through the following specific aims:

**Aim # 1:** Compare subject reported outcomes of pain, function and level of activity for all subjects before and after treatment. Follow the subjects for 24 weeks by clinic visits and phone surveys.

**Aim # 2:** Compare the changes in perifascial lesion volume for all subjects before and after treatment by diagnostic ultrasound imaging. Follow the subjects for 12 weeks by clinic visits.

**Aim # 3:** Evaluate the tolerability and safety of ITU for the treatment of the chronic plantar fasciitis.

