#### Aim 2: Assessment of Perifascial Hypoechoic Lesions

Diagnostic ultrasound imaging will be performed with an FDA 510(k) cleared ultrasound scanner (Spark® System, Ardent Sound, Inc. – Mesa, AZ, see Appendix 5) using a coupling gel (Polysonic® Parker Laboratories, Inc., Fairfield, NJ, see Appendix 6) by a trained sonographer or physician. The subject will positioned prone on an exam table with the feet over the edge of the table. The plantar fascia of the affected and contralateral feet will be imaged. The thickness and depth of the fascia as well as the size and location of any hypoechoic lesion(s), when present, will be recorded using both long and short axis imaging. Change in the volume of hypoechoic plantar fascial lesions relative to the baseline measurement will be calculated.

[figure not shown]
[figure not shown]

Figure 4: representative long and short axis ultrasound images

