##### Image Storage & Cine

- Dicom Compatible
- Stores Images and Cine as Raw Data
- Export Images as bmp or jpg
- Export Cine as AVI
- Back-up Database to internal or external Hard Drive, CD, DVD or Network

**Power: 100-240 VAC  
50-60 Hz input**

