TITLE: Preliminary Protocol for Intense Therapeutic Ultrasound for the Treatment of Chronic Plantar Fasciitis

PROTOCOL NO.: WIRB® Protocol #20160753

DATE: May 26, 2016

SPONSOR: Guided Therapy Systems

[name]

[name]

INVESTIGATOR: [name]

[name]

[name]

Statistical Approach:

- Pain Reduction:

Pain level at the plantar fascia was self-reported by subjects at pre-treatment (used as baseline measurement) and again at each follow-up - 4, 8, 12, and 26 weeks - after initial treatment. The pain scale subjects used to identify their level of pain was a 10-point pain scale range, where 0 = no pain, 1 = slight pain through 10 which equates to the patient's worst imaginable pain. The goal for all subjects in the treatment group was to reduce pain by at least 25%. For patients reporting an initial (baseline) score ranging 6-10, this reflects a VAS pain score reduction  $\geq$  a 2 point drop; for initial scores ranging 2-5, this reflects a VAS pain score reduction  $\geq$  a 1 point drop. Pain scores reported at follow-up timepoints were compared to baseline score for each subject to determine if the goal was met by dividing the difference in the follow-up and baseline pain score by the baseline pain score. The percentage of subjects that met the pain reduction goal was calculated at each timepoint for both control and treatment groups by dividing the number of subjects that achieved the pain reduction goal at each timepoint by the total number of patients that gave a pain score for that time point.

- Plantar Fascia Hypoechoic Lesion Size:

A large proportion of patients suffering from chronic plantar fasciitis present with hypoechoic lesions in or around the proximal plantar fascia, as viewed by diagnostic ultrasound imaging.

Hypoechoic lesions were imaged and volumes were calculated at the baseline visit and each follow-up visit by measuring the inferior-to-superior and posterior-to-anterior radii in the long axis and the medial-to-lateral radius of the transverse axis and applying the following formula for the volume of an ellipse:

$$\text{Volume} = (4/3)\pi \cdot r_1 \cdot r_2 \cdot r_3$$

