With  $r_1$ ,  $r_2$ , and  $r_3$  representing the three radii detailed above. Changes to lesion volumes were recorded at each follow-up timepoint and compared to baseline by dividing the volume of the lesion at that timepoint with the volume of the same lesion at pre-treatment baseline.

- Foot Function Index Score Reduction:

In addition to the 10-point VAS pain scale, patients self-reported answers to questions from the Foot Function Index (FFI) pain subscale questionnaire, which has been standardized in a number of PF-focused publications . Scores range from 0-90, with 0 indicating no pain and 90 indicating the worst pain imaginable in a variety of daily activities involving use of the plantar fascia. Self-reported scores were taken at baseline and each follow-up timepoint. The average score for each timepoint were calculated, and follow-up averages were compared to baseline to calculate the percentage reduction in score.

- Hypoechoic Lesion Size – Pain/Function Correlation:

To determine the strength of a linear relationship between pain/function score reduction and lesion size reduction, linear regression was performed. Patient data related to pain/function score reduction at each follow-up timepoint compared to baseline were matched with corresponding data related to lesion size reduction. The average pain reduction percentage for each follow-up timepoint was paired with the average lesion size reduction percentage for the same follow-up timepoint to generate a data point for linear regression and the Pearson-correlation coefficient ( $r$ ) calculation.  $R$ -values found between 0.6 and 0.8 were considered strong and  $>0.8$  were considered very strong.

- Statistical Calculations

Student T-tests were utilized to determine statistically significant differences between baseline and subsequent follow-up measurements for self-reported and lesion size measurements. All error bars displayed in graphs are standard error. The level of significance ( $\alpha$ ) was set to 0.05.

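### No masked or independent reading of lesion volume is described, so a small directional tilt in the radii could pass for shrinkage after treatment

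*SAP*

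**What the plan says.** - **How volume is obtained.** The SAP, under Plantar Fascia Hypoechoic Lesion Size, states: "Hypoechoic lesions were imaged and volumes were calculated at the baseline visit and each follow-up visit by measuring the inferior-to-superior and posterior-to-anterior radii". The third dimension is "the medial-to-lateral radius of the transverse axis". The three radii are multiplied, "applying the following formula for the volume of an ellipse", that is (4/3)π·r1·r2·r3.
- **How change is expressed.** By "dividing the volume of the lesion at that timepoint with the volume of the same lesion at pre-treatment baseline".
- **Who images.** Protocol Aim 2 asks for imaging "by a trained sonographer or physician" and sets no condition of independence. The Responsibility column of the protocol's Timeline carries the same entry for the ultrasound imaging row and the ITU row: GTS or the principal investigator. The SAP header reads "SPONSOR: Guided Therapy Systems", and the protocol's Interventions section names that company as the source of the treatment system.
- **How it is tested.** Aim 2 in Materials and Methods is to "Compare the changes in perifascial lesion volume for all subjects before and after treatment by diagnostic ultrasound imaging". The protocol's Statistical analysis section uses paired t-tests, and the SAP uses Student t-tests against baseline. Both set α = 0.05.
- **What is not described.** Neither document mentions masking of the image reader, an independent or central reader, a random reading order, repeat reads, or intra- or inter-reader error.
- **What the scanner can do.** The brochure in protocol Appendix 5 says that the system "Stores Images and Cine as Raw Data".

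**The concern.** The radii are judgements about where the edge of a dark area lies on an ultrasound image. Under the plan as written, the measurements belong to successive visits, the treating side is responsible for the imaging, and the follow-up reader has to find again the lesion seen at baseline. A reader in that position could, without intending it, place the edges slightly tighter after treatment. Because volume is a product of three radii, a tilt shared by all three is roughly tripled in the result.

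The weight of this comes from the part that lesion volume plays. Subjects know that they were treated, so their pain and function scores are open to expectation. Clinical grading and a structured examination are collected, but neither the protocol's Statistical analysis section nor the SAP says how they would be analysed. Lesion volume is the only outcome in those two sections that subjects do not report, so its main value is as corroboration. That value falls if the reading could lean in the same direction as the self-reports.

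**Working it through.** The documents give no effect size, SD, reader error or power calculation for lesion volume, so there is no figure of the plan's own to reproduce.

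**Inputs from the documents:** the volume formula and the follow-up/baseline ratio (SAP); α = 0.05, taken as two-sided because no side is stated; up to 30 subjects (protocol, Selection of Subjects); imaging at weeks 0, 4, 8 and 12 (protocol, Outcome measures and Timeline).

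**Assumed inputs:** the size of the tilt, and the between-subject SD of the log volume ratio.

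**Step 1. Tilt to apparent shrinkage.** If every follow-up radius is read short by a fraction b and nothing has truly changed, the ratio is (1 − b)³.

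| b per radius | Ratio | Apparent shrinkage |
|---|---|---|
| 2% | 0.98³ = 0.941 | 5.9% |
| 5% | 0.95³ = 0.857 | 14.3% |
| 10% | 0.90³ = 0.729 | 27.1% |

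If only one radius is tilted by 5%, the ratio is 0.95 and the apparent shrinkage is 5%.

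**Step 2. The reverse question.** A shrinkage s needs b = 1 − (1 − s)^(1/3). For 10%, b = 3.4% to 3.5%. For 25%, b = 9.1%. For 50%, b = 1 − 0.5^(1/3) = 20.6%.

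**Step 3. Random error alone.** With three radii at each of two visits and a coefficient of variation CV per radius, the SD of the log ratio is √6 × CV: 0.12 at 5% and 0.24 at 10%. In simulation the median ratio stays at 1.00, and the mean ratio rises slightly, to 1.007 and 1.03. Undirected error does not create shrinkage.

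**Step 4. Effect on the test.** This uses a paired t-test on the log ratio with mean 3·ln(1 − b), by the noncentral t distribution, taking every lesion as still measurable at follow-up. For b = 5%, 3·ln(0.95) = −0.154. With n = 30 and SD 0.3, the noncentrality in absolute value is 0.154/0.3 × √30 = 2.81. The protocol's Background reports a lesion in 68% to 84% of patients (it words the lesion as hyperechoic). Of 30 subjects that is about 20 to 25, and it is used here only to set the lower n. Chance of p < 0.05 with no true change, per test:

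| n | b | SD 0.2 | SD 0.3 | SD 0.4 | SD 0.6 |
|---|---|---|---|---|---|
| 20 | 2% | 25% | 14% | 10% | 7% |
| 20 | 5% | 90% | 59% | 37% | 19% |
| 30 | 2% | 36% | 19% | 13% | 8% |
| 30 | 5% | 98% | 78% | 53% | 27% |

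The nominal rate is 5%. A larger n raises these figures, because the tilt is systematic.

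**Step 5. With masked reading.** If the reader cannot tell the visits apart, a constant reading tilt c applies to all of them, and the ratio is (1 − c)³/(1 − c)³ = 1.00. The false-positive rate from this source returns to 5% per test.

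**The case against.** **Silence is not a statement that readers were unmasked.** This stands. The Timeline column allocates responsibility; it does not record who places the calipers. It allows one person to treat and another to image, although nothing requires that. The SAP says to which visits the volumes belong and does not clearly exclude later reading from stored files. A reader might infer that the documents show measurements made by treating staff who knew the visit and the baseline value. They do not say so. The inference is strong, because the same lesion has to be found again, but what can be asserted is that no masked or independent reading is described.

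**The bias is hypothetical in size and direction.** This also stands. Every tilt and SD above is assumed. The larger effects need all three radii to move together, and the chance of false significance at a 5% tilt runs from 98% down to 19% across the assumed SDs and sample sizes. Nothing in the documents supports saying that readings always lean towards shrinkage, or that a caliper reading is as suggestible as a pain score.

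**Lesion volume is not the primary outcome.** Correct. The protocol's Purpose of Study section names clinical grading and questionnaires as primary and adds imaging to them. The investigator's grading and examination have no masking described either. This limits the weight of the point but does not remove it, because those assessments do not reach the analysis sections.

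**Masked reading does not solve the design problem.** True. Subjects also receive a boot, an orthotic insert and massage, and the comparison is before versus after.

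**Conclusion.** The concern holds as a risk that the plan leaves open and could close cheaply. With no true change, an assumed tilt of 2%, 5% or 10% in every follow-up radius would appear as a shrinkage of about 6%, 14% or 27%, and the paired test would treat it as real change. These figures rest on a tilt that runs in one direction and is common to the three radii; random error does not produce it.

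Two stronger conclusions are not supported. One is that an observed shrinkage would be an artefact: a halving would need about 21% per radius, which is no small tilt. The other is that lesion volume cannot corroborate the self-reports: its value for that is weakened, not abolished.

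One ambiguity bears on the remedy. The SAP refers to control and treatment groups for the pain goal, while the protocol describes a single treated cohort. If a control group exists, the reader should be masked to group as well as to visit.

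**What to change.** Add to protocol Aim 2 and to the SAP's lesion-size paragraph:

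1. Long- and short-axis images, and cine, are stored for every imaging visit. Appendix 5 shows only that the scanner can do this, so the protocol has to require it.
2. After a subject's last imaging visit, the radii used for analysis are measured from the stored files in random order, with date, visit number, subject identity and (if there is a control group) group hidden. Lesions are labelled by location only, so that follow-up and baseline can still be matched.
3. The reader is an existing sonographer or physician, where possible one who did not deliver that subject's ITU.
4. Measurements made on the day remain for clinical use but are not the analysed values.

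The SAP is written in the past tense. If imaging is already complete, masked re-reading is still possible wherever the files were kept.

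**Cost.** Wording in two documents, and time to de-identify and re-measure at most 30 × 4 = 120 image sets. No extra scan, visit, subject or staff member is needed.

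**What remains.** Image acquisition and the choice of plane stay unmasked; stored cine helps only in part. A reader who acquired the images may recognise some of them. Both should be stated as limitations, together with the fact that masked reading does not by itself allow shrinkage to be attributed to ITU in a before-after design.

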#### Statistical analysis

Data will be assessed for variance homogeneity and normality. FFI-P scores, PFCAT, FAAM scores before and after intervention will be compared using a paired t-test. Perifascial lesion volume is measured before and at each post treatment clinical visit using diagnostic ultrasound imaging, and paired t-tests will be utilized for comparison. For determination of statistical significance, a cutoff value of  $\alpha=0.05$  has been selected prior to start of data analysis.

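### The SAP's lesion measure, a ratio to the same lesion's baseline, cannot count new lesions or lesion-free subjects, and no rule says how several lesions in one subject are combined

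*SAP*

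**What the plan says.** The SAP, under Plantar Fascia Hypoechoic Lesion Size, computes an ellipsoid volume from three radii for each lesion. Changes are then "compared to baseline by dividing the volume of the lesion at that timepoint with the volume of the same lesion at pre-treatment baseline". This is the only lesion-change measure that the SAP defines. Its correlation section takes the average percentage reduction in lesion size at each follow-up and pairs it with the average pain reduction.

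The protocol is broader. Aim 2 reads "Compare the changes in perifascial lesion volume for all subjects before and after treatment by diagnostic ultrasound imaging". The Aim 2 imaging section allows for none, one or several lesions: "the size and location of any hypoechoic lesion(s), when present, will be recorded using both long and short axis imaging". It also states "The plantar fascia of the affected and contralateral feet will be imaged", without saying which foot enters the outcome. It then says "Change in the volume of hypoechoic plantar fascial lesions relative to the baseline measurement will be calculated", without saying whether the unit is the lesion or the subject.

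The tests are described separately. In the protocol's Statistical analysis section: "Perifascial lesion volume is measured before and at each post treatment clinical visit using diagnostic ultrasound imaging, and paired t-tests will be utilized for comparison". The SAP's Statistical Calculations section uses Student t-tests of baseline against follow-up lesion size. Neither document names the unit of analysis for these tests, and neither has a rule for a new lesion, for a subject without a baseline lesion, or for several lesions in one subject.

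**The concern.** The denominator decides which data can count. Requiring the same lesion at baseline removes two groups by construction: lesions that appear after treatment, and subjects who had none at the start. A new lesion is evidence against benefit, so dropping it moves the reported percentage in one direction only. A subject whose total lesion volume is stable, or even larger, can be reported as having a shrinking lesion.

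Lesion volume is the whole of Aim 2, and the protocol's stated hypothesis includes a decrease in perifascial lesions. The same percentage supplies one axis of the correlation with pain and function, so the omission reaches a second reported result.

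A second gap concerns the t-tests. The ratio is defined per lesion, and the protocol expects that a subject may have more than one. If the tests were also run per lesion, lesions in the same foot would probably be correlated and the standard error would be too small. The plan does not say whether this is done.

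**Working it through.** The documents give no effect size, SD, lesion count or power for this outcome, so there is no figure of the plan's own to reproduce.

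**1. New lesion.** The SAP ratio is V(follow-up) / V(baseline, same lesion). For a new lesion the denominator is 0 and the ratio is undefined. Two illustrations with invented volumes in mm3:

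| | Baseline | Follow-up, old lesion | Follow-up, new lesion | Same-lesion ratio | Ratio of totals |
|---|---|---|---|---|---|
| A | 60 | 30 | 30 | 30/60 = 0.50 | (30+30)/60 = 1.00 |
| B | 200 | 100 | 150 | 100/200 = 0.50 | (100+150)/200 = 1.25 |

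Both are reported as a 50% reduction. In A the total is unchanged; in B it rises by 25%. Because a new lesion can only add volume at follow-up, leaving it out can only make the result look better.

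**2. Subject without a baseline lesion.** With none at follow-up either, the ratio is 0/0; with a new lesion it is a positive volume over 0. Both are undefined, so the subject has no value. The SAP itself says that many patients, not all, have such lesions, so this case is expected. How many of the up to 30 subjects it affects cannot be read from the documents. The Background gives 68% to 84%, but for lesions it calls hyperechoic, whereas the outcome is hypoechoic. If that range were borrowed as an assumption, 30 x 0.68 = 20.4 and 30 x 0.84 = 25.2, so about 20 to 25 subjects would contribute.

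**3. Several lesions in one subject.** Suppose, as an assumption, that the t-test pooled m lesions per subject with within-subject correlation ICC. The two-sided false-positive rate is then approximately 2 x [1 - Phi(1.96 / sqrt(1 + (m - 1) x ICC))].

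| m | ICC 0.3 | ICC 0.5 | ICC 0.8 |
|---|---|---|---|
| 1 | 0.050 | 0.050 | 0.050 |
| 2 | 0.086 | 0.110 | 0.144 |
| 3 | 0.121 | 0.166 | 0.224 |

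Simulated t-tests (20,000 runs, 20 or 25 subjects) gave 0.086 to 0.152 for m = 2 and 0.121 to 0.235 for m = 3. With one value per subject they gave 0.049 to 0.054.

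**4. The replacement on the same cases.** With subject totals, A becomes 60 to 60 (0% reduction) and B becomes 200 to 250 (25% increase). A lesion-free subject becomes 0 to 0, a valid change of 0. For the percentage, let S0 and S1 be the summed totals over n subjects at baseline and follow-up: (S1/n) / (S0/n) = S1/S0. Subjects who are lesion-free at both visits therefore do not alter the percentage. They do pull the mean absolute change towards zero.

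**The case against.** The strongest reply is that the ratio is only descriptive. Both documents describe the t-tests on volume or size, where a zero can be entered, so new lesions and lesion-free subjects need not be lost from the significance test. That stands: for the test this is a missing definition, not a stated error. It does not rescue the percentage shrinkage or the correlation, since the ratio is the only lesion change the SAP defines.

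A second reply is that a subject with no lesion cannot show shrinkage, so restricting the measure to those with a lesion is reasonable. This stands in part. That restriction is a legitimate supporting analysis, but it is not what Aim 2 says, and it does not justify ignoring new lesions in subjects who are included.

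Two stronger readings are tempting. A reader might infer that the SAP treats several lesions in one subject as independent. It does not say so: lesions may be summed or averaged within a subject, or most subjects may have only one, in which case there is no inflation. A reader might also object that averaging raw ratios is lopsided, since 4.0 and 0.25 average 2.125 although one is a fourfold rise and the other a fourfold fall. That is no ground for this change. The asymmetry works against the treatment, and with equal baselines the totals behave the same way: 100 to 400 and 100 to 25 take the total from 200 to 425, again 2.125.

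**Conclusion.** The concern holds for the reported percentage shrinkage and for the correlation that uses it. There the stated rule excludes new lesions and lesion-free subjects by arithmetic, with no assumption needed. It conflicts with the scope of Aim 2, and the omission of new lesions can only favour treatment. The size of the effect in this trial is unknown, because the documents do not say how often new lesions occur; the volumes in the illustrations are invented.

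For the t-tests, the supportable conclusion is narrower. The unit of analysis and the rule for combining lesions are unstated, so within-subject correlation may be ignored. A false-positive rate of roughly 9% to 22%, by the formula, would follow only if lesions were pooled, if subjects had two or three each, and if the correlation were 0.3 to 0.8. All three conditions are assumptions. The documents do not support a claim that the tests are invalid as planned.

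**What to change.** Define the lesion outcome in the SAP as one value per subject per visit: the summed volume of all hypoechoic lesions in the treated foot, with new lesions included and 0 when none is seen. Naming the treated foot also settles which of the two imaged feet counts.

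- Run the paired t-test on the within-subject change in that total, one value per subject.
- Compute the percentage reduction at each visit as 100 x (1 - mean total at follow-up / mean total at baseline). This is the method the SAP already uses for the FFI. Use the result in the correlation, which otherwise would have no defined lesion input.
- Report the number of subjects with a baseline lesion, and the counts of new and fully resolved lesions at each visit.
- Give a supporting analysis limited to subjects who had a baseline lesion.

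The cost is SAP wording only, since the protocol already has the size and location of every lesion recorded. The drawbacks are that the reported shrinkage may be less favourable, and that lesion-free subjects add zero changes to the paired test, which dilutes the mean absolute change. The supporting analysis shows how far that dilution matters.

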#### Aim 1: Subject reported outcomes and structured physical exam

The principal aim of this study is to demonstrate the efficacy of treatment and time course of response to treatment and post treatment regimens using validated subject reported outcome measures assessing pain, function and level of activity and structured physical examination. Subjects will complete validated subject reported outcome questionnaires assessing pain, function and level of activity prior to initiating treatment and at 4, 8, 12, and 24 ( 24 week surveys will be completed by a phone interview) weeks after starting treatment. Subjects will also be contacted 2-3 days following each treatment to assess treatment tolerability and to document and address adverse effects (if any). They will also be contacted by phone 2 weeks after

treatment(s) to assess progress and determine if the boot can be discontinued.

**Pain** will be assessed using the of the foot function index pain subscale (FFI-P) and the subject reported outcome measures (SROM). These two instruments have been used to assess pain in previous studies of plantar fascia treatments. [22, 23]

**Function** will be assessed using two validated PRO instruments the PROMIS PF CAT and the FAAM. The PROMIS PFCAT is a subject relevant outcome measure that uses computer adaptive survey questions to assess the subject's pain and function in relation to daily activities [24]. The FAAM has been shown to be a reliable, responsive, and valid measure of physical function for individuals with a broad range of musculoskeletal disorders of the lower leg, foot, and ankle [25].

**Level of Activity** will be assessed using the activity subscale of FAAM. This subscale scores quantitatively the level of difficulty subjects face when they perform basic activities of daily living. It has shown to be an accurate and reliable predictor of the activity level while performing day-to-day activities [25]

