## Appendix 1-D: Foot function index pain subscale (0 – 10)

How severe is your heel pain?

---

1. At its worst?	No pain	Worst pain imaginable
------------------	---------	-----------------------

---

2. After you get up in the morning with the first few steps?	No pain	Worst pain imaginable
--	---------	-----------------------

---

3. At the end of the day?	No pain	Worst pain imaginable
---------------------------	---------	-----------------------

---

4. When you walk barefoot?	No pain	Worst pain imaginable
----------------------------	---------	-----------------------

---

5. When you stand barefoot?	No pain	Worst pain imaginable
-----------------------------	---------	-----------------------

---

6. When you walk wearing shoes?	No pain	Worst pain imaginable
---------------------------------	---------	-----------------------

---

7. When you stand wearing shoes?	No pain	Worst pain imaginable
----------------------------------	---------	-----------------------

---

8. When walking with orthotics?	No pain	Worst pain imaginable
---------------------------------	---------	-----------------------

---

9. When standing with orthotics?	No pain	Worst pain imaginable
----------------------------------	---------	-----------------------

---

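### The SAP does not carry forward the protocol's function and activity instruments (PROMIS PF CAT and FAAM), and its 'pain/function' correlation is built from pain data only

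*SAP*

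**What the plan says.** **Protocol.** Purpose of Study places subject-reported pain, function and level of activity among the primary outcome measures, together with a clinical grading. Aim 1 assigns the instruments. Pain has the FFI pain subscale (FFI-P) and the SROM questions, function "will be assessed using two validated PRO instruments the PROMIS PF CAT and the FAAM", and level of activity has the FAAM activity subscale. The Statistical analysis section then commits to testing them: "FFI-P scores, PFCAT, FAAM scores before and after intervention will be compared using a paired t-test".

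**SAP.** Under Pain Reduction the measure is a self-reported 0–10 pain scale. Under Foot Function Index Score Reduction, "patients self-reported answers to questions from the Foot Function Index (FFI) pain subscale questionnaire", and "Scores range from 0-90, with 0 indicating no pain and 90 indicating the worst pain imaginable". The section on Hypoechoic Lesion Size – Pain/Function Correlation begins: "To determine the strength of a linear relationship between pain/function score reduction and lesion size reduction, linear regression was performed". It goes on to define each data point as the average percentage pain reduction at a follow-up, paired with the average percentage lesion-size reduction at that follow-up. Statistical Calculations applies Student t-tests to self-reported and lesion-size measurements without listing instruments. Neither FAAM nor PROMIS is mentioned anywhere in the SAP.

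**The concern.** The two documents disagree on which primary domains are analysed. An analyst who follows the SAP has a definition, a scale and a comparison for pain, and nothing comparable for function or activity. The SAP nevertheless uses the word function in a section title and in the stated aim of a regression.

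Two things are at stake. First, protocol primary domains could go unreported, or be reported with scoring and time points chosen after the data are seen. Second, a correlation between lesion shrinkage and pain could be read as evidence that lesion shrinkage tracks function, when no function score enters it.

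**Working it through.** **Step 1: what the FFI score contains.** The inputs are from Protocol Appendix 1-D. The stem over the whole form is "How severe is your heel pain", the form's title gives a 0–10 scale, and the last item is "9. When standing with orthotics", so there are nine items.

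Maximum score = items × item maximum = 9 × 10 = 90.

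This matches the SAP's stated upper limit exactly. The SAP score is therefore the full nine-item pain subscale with nothing added from the function side of the index. Several items ask about pain while walking or standing, so the score is related to activity, but every response is a pain severity and both ends of the scale are pain.

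**Step 2: instruments by domain, protocol against SAP.**

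| Domain (Protocol, Purpose of Study) | Instruments (Protocol, Aim 1) | Test (Protocol, Statistical analysis) | Defined in the SAP |
|---|---|---|---|
| Pain | FFI-P, SROM | FFI-P: paired t-test | FFI-P and a 0–10 pain scale |
| Function | PROMIS PF CAT, FAAM | Both: paired t-test | Neither |
| Level of activity | FAAM activity subscale | FAAM: paired t-test | Not defined |

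Self-reported measures defined in the SAP: 2, of which 2 measure pain and 0 measure function. Function instruments in the protocol: 2, of which 0 are carried into the SAP. The SROM set in Appendix 1-E has one question on improvement in daily function (SROM 5), but the protocol classes SROM under pain and the SAP does not name it.

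**Step 3: what the 'pain/function' regression uses.** The SAP states the aim in terms of pain/function score reduction, but the only quantity it describes pairing with lesion reduction is average pain reduction. Whether that average comes from the 0–10 scale or from FFI-P is not stated. By Step 1 both are pain scores, so the conclusion is the same.

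**Step 4: when the missing instruments are collected.** The documents do not agree. Protocol Outcome measures gives weeks 0, 4, 8 and 12 in clinic and the same questionnaires by phone at weeks 2 and 24, which is six occasions. Aim 1 gives baseline and weeks 4, 8, 12 and 24, which is five. The Timeline row also shows five, but describes the survey as a pain scale and an ankle mobility scale and names neither PROMIS nor FAAM. The SAP gives its last follow-up as week 26.

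**The case against.** The strongest reply is that the analysis is planned. The protocol commits to paired t-tests on PFCAT and FAAM, nothing in the SAP withdraws them, and the SAP's t-test sentence covers self-reported measurements without restricting them to pain. This stands in part. A reader might infer that function and activity will have no result at all; the documents do not support that, because the protocol's commitment remains. The general sentence does not close the gap, however. It gives no score or time point for either instrument, and FAAM allows a not-applicable answer (Appendix 1-B), so a scoring rule is needed.

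A second reply is that the SAP is open about the FFI: it calls it a pain subscale, gives it pain anchors, and nowhere claims that function improved. That is fair. The mislabelling is confined to the correlation section's title and the phrase pain/function, and the documents do not show that anyone mistook the index's name for its content.

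Three stronger readings are tempting and do not hold:

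- **That the 0–10 scale and FFI-P must agree by construction.** They are separate instruments and neither is computed from the other. They are likely to be correlated, but the SAP does not present them as independent confirmation.
- **That FAAM is counted twice, for function and for activity.** Function also has PROMIS. The copy of Appendix 1-B available here has a figure not shown after item 21, so it cannot be said that the form has no further items.
- **That adding the FAAM and PROMIS tests would answer the hypothesis of a faster return to activities.** A paired change from baseline involves no comparator, so it cannot show that anything was faster.

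**Conclusion.** The point holds as a protocol–SAP mismatch on primary outcomes. Two of the three questionnaire domains, function and level of activity, have no defined analysis in the SAP, although the protocol plans one. The SAP's one analysis with function in its title uses pain data only, so a result reported under that title would be a pain result.

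The size is a count: 0 of 2 function instruments carried forward, and 9 of 9 FFI items on pain. No sample size, test or numerical result in the plan is shown to be wrong. The conclusion rests on the text of the two documents and assumes that the SAP is meant to set out the analysis of the protocol's primary questionnaire outcomes. If function was dropped on purpose, the SAP should say so and give the reason.

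**What to change.** In the SAP:

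1. Label the FFI outcome as the FFI pain subscale, and replace pain/function with pain wherever only the 0–10 scale or FFI-P is used. State which of the two enters the correlation.
2. Add the paired change-from-baseline analyses of the FAAM and PROMIS scores that the protocol already plans, and make them the only source of any statement on function or activity. Give the score used, the FAAM rule for not-applicable answers, and the PROMIS score meant (Aim 1 says PF CAT, while Appendix 1-A is headed LE CAT).
3. Run them at the visits where the instruments were in fact collected, after reconciling Outcome measures, Aim 1, the Timeline and the SAP's own follow-up weeks.

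The cost is wording plus two more paired analyses on data that the protocol already collects. The function result may be less favourable than the pain result. There are also more unadjusted tests. With the SAP's four follow-ups, self-reported tests go from 2 × 4 = 8 to 4 × 4 = 16. If all tests were independent at 0.05, the chance of at least one false positive would go from 1 − 0.95^8 = 0.34 to 1 − 0.95^16 = 0.56. Independence is an assumption, and scores from the same subjects are correlated, so the true figures would normally be lower. The protocol already commits to testing these instruments, so this is not a reason to leave them out of the SAP.
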